Initial treatment of urinary incontinence typically starts with non-invasive measures, due to the fact that related benefits are associated with low risks and limited expenses. These measures include lifestyle modifications, such as weight loss, smoking cessation, treatment of obstipation, alcohol- and caffeine-restriction, avoidance of excess fluid intake and fluid- and voiding-management. Systematic reviews report that pelvic floor exercises in women with IU are beneficial (Hay-Smith EJ *Cochrane Database Syst Rev.* 2011). A systematic review found that 59% of women with stress urinary incontinence were cured after 12 months of supervised pelvic floor muscle training. (RiemsmaR,HagenS, *BMC Med.* 2017).

Treatment of SUI aims at strengthening the pelvic floor and stabilize urethral mobility. Non-invasive treatment of SUI includes pelvic floor muscle training and use of vaginal devices. There are studies that indicate that bladder control pessaries are effective and may be preferable for women, who have SUI during specific situations as for example, during exercise (Lipp A, *Cochrane Database Syst Rev* 2014.) Furthermore, there are over-the-counter vaginal devices, such as Contrelle® or Impressa® that are SUI specific, and may be better tolerated as they are easier to self- administer. Women with symptoms of SUI in spite of conservative non-invasive treatment may be candidates for surgery. Currently, the most commonly performed surgery for SUI is the midurethral sling, a 30-minute outpatient procedure in which a synthetic mesh sling is placed through either a retropubic or transobturator approach. (Nager CW. *Am J Obstet Gynecol.* 2016). The midurethral sling is the most extensively studied procedure for SUI, with documented short-term efficacy (>5 yrs.) between 43- 92% (Ford AA, *RCochrane Database Syst Rev.* 2015// Schimpf MO, *Am J Obstet Gynecol.* 2014). Complication rates of this procedure is low, but includes risk of bladder- or

urethral lesion, urinary retention, haematoma, pain, worsening of urgency, dyspareunia and sling erosion (Ford AA, *R Cochrane Database Syst Rev*. 2015// Morling JR, *Lancet*. 2017// Anger JT, *Urology*. 2014)

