A novel minimal-invasive method of treating UI, has been introduced in the recent years, namely vaginal laser treatment. The use of laser has now been described in pelvic organ prolapse, UI and genito-urinary symptoms of menopause. Bhide et al have recently published a review article, where they describe 5 prospective cohort studies of laser-treatment of SUI (Table 1) (Bhide AA, *Int. Urogyn. Journ.*, 2018). Gambacciani et al. published a study of 45 women with IU, of whom 19 had SUI (Gambacciani M, *Ital J Gynaecol Obstet*. 2015). Vaginal treatment included application of YAG laser 3 times with 1 month apart and symptoms were evaluated at baseline and at a 3- and 6-month follow-up with ICIQ-U1 SF questionnaire. The treatment induced a significant decrease in ICIQ-U1 at 3 months with decrease of ICIQ scores from 12.0+/- 1.8 to 5.6+/-2.6 and this was still significant at 6 months. Ogrinc et al published a study on the use of YAG laser on women with IU, of whom 115 had SUI. Symptoms were evaluated at baseline and at 12-months follow-up with Incontinence Severity Index (ISI) and all women showed significantly decreased ISI scores (Ogrinc UB, *Lasers Surg Med*. 2015). Fistonic et al published two studies of the use of a single application of YAG laser in the treatment of SUI and evaluated with ICIQ-U1 SF. The first study evaluated 31 women with SUI and follow-up at 1- 2- and 6- months showed significantly reduced ICIQ-IU SF scores albeit many of women were lost to follow-up (Fistonić N., *YAG. Lasers Med. Sci.* 2016). The next study of 73 women with SUI showed 72.3% experiencing improvement of symptoms, 23.4% experiencing no change and 4.3% experiencing worsening (Fistonić N, *Climacteric*. 2015). Pardo et al. evaluated the vaginal erbium:YAG laser in a longitudinal prospective study in 42 patients with SUI (Pardo JI, *Eur J Obstet Gynecol Reprod Biol*. 2016). Treatment was applied twice with 21- 28 days apart and median ICIQ-IU SF scores, which was reported at 3- and 6- months follow-up, was significantly reduced; 78.6% reported improvement of SUI and 38.1% reported a complete remission of SUI. Gambacciani et al. studied 205 post-menopausal women of which 114 were diagnosed with SUI. In this study, three vaginal erbium:YAG laser applications were administered at 30-day intervals, and ICIQ-SF was used to evaluate before and after treatment with follow-up up to 24 months post treatment (Gambacciani M, *Climacteric*. 2018). The results demonstrated a significant decrease in ICIQ-SF scores from baseline to 12 months post treatment. However, at 18 and 24 months, ICIQ-SF scores were not significantly different from baseline. All 5 studies used a non-randomised selection of patients and treatment effect was estimated by using pre-treatment incontinence scores for comparison . Only the YAG laser has been evaluated in a randomized trial with 114 women which found significant improvement in the ICIQ-SF scores in the treatment arm compared with placebo (Bleganje 2018). None of the mentioned studies showed any serious complications or side effects of the laser treatment.

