The study will take place in the department of Gynecology and Obstetrics of Hvidovre University Hospital, Copenhagen Denmark in the period of May 2019 to May 2020. Inclusion criteria for the study cohort and controls will be patients i. referred from specialist gynecologists or GPs with SUI; ii. speak and understand Danish; iii. has a voiding diary that indicates stress incontinence; iv. older than 18 years of age; vii. with BMI under 35; viii. and present with mild to severe SUI evaluated after ICIQ-SF (slight (1-5), moderate (6-12), severe (13-18) and very severe (19-21), Kloving 2009). Exclusion criteria presence of pelvic organ prolapse greater than stage II by the POP-Q system, previous pelvic surgery, current infections, keloid formation, vaginal pain, dyspareunia and ongoing pregnancy.

Interventions

In this study, women will receive a series of three treatments using a fractional (pulsed) CO₂ laser system (SmartXide² MonaLisa Touch, DEKA M.E.L.A Srl, Florence, Italy), each performed in an outpatient setting without analgesia. A tubular laser-probe is inserted in the vaginal canal until reaching the vaginal vault. A burst of laser pulses is transmitted through the probe and deflected at 90° in four directions towards the vaginal wall, then rotated 45° for a second burst of pulses. Guided by markings on the probe, it is withdrawn

4mm and the procedure is repeated until reaching the introitus. Treatment parameters include power 30W, dwell time 1000 μ s, 1000 μ m spacing, using normal scan mode, with Smartstack setting for 1 at first application and 3 for the next two applications.

Both study- and placebo- treatments will be performed by specialist gynecologists employed in the department. Patients, who meet inclusion criteria and consent to study participation, will be randomized by computer service [REF] to conservative treatment, which encompass local estrogens (Vagifem 10 μ g twice weekly) if relevant (postmenopausal women) and pelvic floor training supervised by specialised physiotherapists in our own institution, whilst the study cohort will receive the same treatment with the addition of transvaginal laser applied thrice with 25- 45 days apart (CO₂ laser- treatment (DEKA SmartXide² Laser System, MonaLisa Touch). The controls will receive placebo treatment, with the use of the inactive laser, but relevant sound effects.

Outcomes

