Primary outcome of the study is patient experienced improvement of SUI evaluated by standardized ICIQ-SF questionnaire.

Our secondary outcome is objective improvement as measured by standardized stress test performed by specialist nurse before treatment and 1-2 month after last laser or placebo treatment. The bladder is emptied with a catheter and 300ml of saline is inserted. The patient is then stood up wearing a pad with legs slightly apart and asked to forcefully cough 3 timers. The examiner registers whether there is incontinence as either yes or no as well as grams of urine leakage in the pad. Furthermore, side- effects both positive and negative as well as patient satisfaction will be registered by the use of patient questionnaires at 1-2 months post treatment.

Participant timeline

Timeline after inclusion

- 1st visit in outpatient clinic: evaluation by nurse or physician; instruction in minimal care treatment, pelvic examination, evaluation of bladder diary, evaluation of study eligibility and randomization. Baseline information registered in case report form and referral to physiotherapy.
- 2nd visit. 1st Laser/placebo treatment
- 3rd visit 2nd Laser/placebo treatment (between 20 and 40 days after previous treatment)
- 4th visit 3rd Laser/placebo treatment (between 20 and 40 days after previous treatment)
- 5th visit. Follow up 1-2 months after last treatment. ICIQ-SF questionnaires, clinical examination and standardized stress test. Information registered in case report form.

Both study-cohort and controls will receive pelvic floor training supervised by specialised physiotherapists. If the treatment is evaluated as unsuccessful, next treatment option will be considered.

4. Sample size

Based on variation and observed effect of more than 2 points from other studies (Blagajna 2018) on the ICIQ-UI SF scale we have calculated that 20 patients in each group would be sufficient even with 20% dropout to show a difference. The assumptions are significance level of 0,05 and a risk of type 2 error set to 20%.

Recruitment

All urogynecologist and specialised urogynecological nurses at the department will be actively involved in the study and will be actively including patients.

Methods: Assignment of interventions (for controlled trials)

Sequence generation

A computer will generate the numbers using blocks of 6.

Allocation concealment mechanism

Allocation will be hidden in a computer program.

Implementation

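### Is the sample size too small because both arms receive supervised pelvic floor training, while the planning effect comes from a laser-versus-placebo trial?

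*Protocol*

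**What the plan says.** The planning effect in section 4 (Sample size) is "Based on variation and observed effect of more than 2 points from other studies", with one randomised trial cited. With a significance level of 0.05 and a type 2 error of 20%, the protocol concludes that "20 patients in each group would be sufficient even with 20% dropout to show a difference". No SD is printed. Twenty per group less 20% leaves 16 evaluable per group.

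The Introduction gives the cited trial one sentence: 114 women, YAG laser, and it "found significant improvement in the ICIQ-SF scores in the treatment arm compared with placebo". It says nothing about background treatment.

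In this trial, controls receive conservative care with an inactive laser, "whilst the study cohort will receive the same treatment with the addition of transvaginal laser applied thrice" (Interventions). The Participant timeline repeats that "Both study-cohort and controls will receive pelvic floor training supervised by specialised physiotherapists". On training itself, the Introduction cites a review in which "59% of women with stress urinary incontinence were cured after 12 months of supervised pelvic floor muscle training".

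The primary analysis is a t-test on post-treatment ICIQ scores, read 1-2 months after the third treatment.

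**The concern.** The trial measures what laser adds to supervised training. If the borrowed effect was seen in women who did not train, it may be too large for this setting. A woman made dry by training has nothing left for the laser to improve, and she pulls the group difference towards zero. Section 4 allows for dropout but not for this. If the dilution were large, a null result would be likely even with a laser as good as in the cited trial, and it could be misread as evidence of no effect.

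**Working it through.** **Inputs.** From section 4: 20 per group, 20% dropout, alpha 0.05, power 80%, planning difference 2 points. Two-sided testing is assumed, because sidedness is not stated. The cure shares c = 20% and 30% are assumptions; c = 59% is the 12-month figure in the Introduction.

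**The plan's own figure.** Without an SD, 20 per group cannot be reproduced directly. Solving backwards with the noncentral t for n = 16 per group and 80% power gives a standardised difference of 1.024. For a 2-point difference this means an SD of 2 / 1.024 = 1.95.

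**Simple dilution.** If a share c in each arm is cured by training and gains nothing from laser, and the SD does not change, the standardised difference becomes 1.024 x (1 - c):

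| c | Difference (points) | Standardised | Power, n = 16 | Evaluable per group for 80% |
|---|---|---|---|---|
| 0 | 2.00 | 1.024 | 80% | 16 |
| 20% (assumed) | 1.60 | 0.819 | 61% | 25 |
| 30% (assumed) | 1.40 | 0.717 | 50% | 32 |
| 59% (12 months) | 0.82 | 0.420 | 21% | 91 |

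Dividing by 0.8 for dropout and rounding up gives 32, 40 and 114 randomised per group.

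**Does 59% apply at the read-out?** There are two gaps between treatments, of 20-40 days (Participant timeline) or 25-45 days (Interventions), followed by 1-2 months. The shortest path is 2 x 20 + 30 = 70 days and the longest 2 x 45 + 60 = 150 days after the first treatment. Training starts by referral at the visit before, and that interval is not stated. The read-out is still likely to fall well short of 12 months, so 59% is an extreme scenario.

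**Can the SD stay fixed?** Not if cured women score 0. With a share c at zero, and the uncured having mean m and SD s, the arm variance is (1 - c)s² + c(1 - c)m². Take c = 0.30, s = 1.95, m = 5.6 for controls and m = 3.6 with laser (values assumed for illustration):

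- Controls: 0.7 x 3.80 + 0.21 x 31.36 = 9.25
- Laser: 0.7 x 3.80 + 0.21 x 12.96 = 5.38
- Pooled SD: √((9.25 + 5.38) / 2) = 2.70
- Standardised difference: 1.40 / 2.70 = 0.518

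Power is then 29% at 16 per group, against 50% in the table. At 32 per group it is 53%, and 80% needs about 60.

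**In the other direction.** If the laser effect adds fully to training, power stays at 80%. If N was set for 2 points but the true effect in the cited trial is larger, then with SD 1.95 and n = 16:

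| True effect | Power, c = 20% | Power, c = 30% |
|---|---|---|
| 2.5 points | 80% | 69% |
| 3 points | 92% | 84% |

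For c = 30%, then, defensible assumptions give anything from 29% to 84%. The documents do not let one choose among them.

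**The case for a change.** The strongest case for acting is that the protocol itself credits training with substantial cure, gives training to everyone, and attaches no planning input to the comparison it will make. Even a 10% cure share takes power to 71% (1.024 x 0.9 = 0.921). Holding the SD fixed favours the sponsor, since zeros widen it. The remedy also looks cheap: say whether the cited trial gave training, or call 20 per group a feasibility number.

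Much of this stands. The arithmetic is right under its assumptions, and section 4 is silent on the point. Three things limit it.

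- The mismatch is not shown. Both trials compare laser with placebo. The only possible difference is background training in the cited trial, on which the documents say nothing. If its women trained too, this dilution does not arise.
- The model needs cured women to score exactly 0, the same share in both arms, and no laser benefit in them. The Introduction does not define cure. That the lowest severity band starts at 1 is a statement about eligibility and does not define cure in the cited review. The protocol also proposes a separate mechanism for laser, collagen remodelling, so at least partial additivity cannot be excluded.
- No alternative N is better founded. Thirty-two evaluable per group rests on an assumed 30% and on a fixed SD that the same premise contradicts.

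**Conclusion.** The concern does not call for a change. Section 4 leaves one premise unsaid: that an effect of about 2 points holds over and above supervised training. The stated 80% is conditional on that effect, as any power figure is, and nothing in the protocol shows it to be false. The falls to 61% and 50% rest on assumed cure shares of 20% and 30% with an unchanged SD. The fall to 21% also applies a 12-month rate to an outcome read about 70 to 150 days after the first treatment.

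Enlarging the trial on this basis would mean 32 to 114 randomised per group instead of 20, at a single centre in about a year, for a number no better supported than the present one. Giving up the power claim on an assumed dilution model is something statisticians could reasonably dispute.

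The comparison itself is sound: training is given to both arms, so it does not bias the contrast between laser and sham. A reader of a null result can judge from the estimate and its confidence interval what has been excluded. The unprinted SD is a separate matter that does not depend on this argument: with the post-treatment SD of 2.6 in "decrease of ICIQ scores from 12.0+/- 1.8 to 5.6+/-2.6", from an uncontrolled cohort, power for 2 points at 16 per group would be 56% with no dilution at all.

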The data manager will do the sequence generation. Doctors at the urogynecological clinical will enroll patients and assignment will occur when patient data is submitted in the electronical case report form.

Blinding (masking)

The patient and the outcome assessor (nurse) will be blinded. However, the doctor performing the laser treatment cannot be blinded.

Unblinding will occur if a patient suffers adverse events that requires treatment or exclusion of the trial.

Methods: Data collection, management, and analysis

Data collection methods

Baseline data will be recorded: age, BMI, parity, ICIQ-UI SF, standardized stress test, degree of pelvic prolapse. All data will be saved in RedCAP, which will provide facilities for randomization as well as ensure that data are being stored according to Danish legislation.

ICIQ-UI SF is a validated scale for measuring degree of stress incontinence and has been used in many studies.

Data collection forms will be constructed in RedCap.

Both the study cohort and controls will be contacted by telephone, if they do not come for follow-up treatment or data-collection.

Nurses will be instructed in the standardized stress test.

Statistical methods

The post treatment scores will be compared using Students t-test for the primary outcome and chi square test for dichotomous outcomes. Our strategy is an intention to treat analysis when possible. Clinically significant differences of our primary outcome is probably at least 2 points.

Methods: Monitoring (6)

Data monitoring

All investigators will be part of the monitoring board and will decide whether the trial should be terminated. No interim analysis are planned due to the few patients involved.

Harms

All harms will be reported verbatim. Serious adverse events will be discussed by the monitoring board within two work days.

Auditing

No auditing is planned as the procedures and measurements will be carried out by very few health workers.

Ethics and dissemination

Research ethics approval

Relevant approvals from ethics committee and data protection agency will be obtained.

Protocol amendments

Protocol amendments will be reported to ethics committees and trial registries.

Consent or assent (12)

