Written and oral consent will be obtained and documented recruiting gynaecologist or specialized nurse in the outpatient clinic. At the clinic patients are attended individually in a separate room. If they are interested they will be scheduled for treatment. In the mean time they can consult with their doctor or family.

Confidentiality

Data will be collected, stored and reported in accordance with Danish legislation and approval from the data protection agency will be obtained.

Declaration of interests

All investigators will have to provide a declaration of interest before the study begins. Investigators with conflicts to the manufacturer of the Laser device will not be able to participate in this study.

Access to data

Only investigators will have access to data. Data will either be anonymized or destroyed a few years after the study finishes.

Ancillary and post-trial care (11, 15)

As this treatment is already being used in Denmark, patients that suffer damage will be eligible to compensation through the 'Patienterstatningen'.

No participation fee for participant will be given.

Dissemination policy (13)

Results will be reported in peer reviews journals and the study results will be registered at clinicaltrials.gov.

Professional writes will not be used. We will share our data to the extent it does not interfere with privacy and Danish legislation.

Economy (10)

Hvidovre hospital has so far funded the project with 60.000. The project has been initiated by the authors of the protocol. Additional funding will be sought to employ a PhD student for managing data, doing analyses and writing the paper. The department will pay for salary of the nurses and treating physicians and the Laser is already at our institution.

Additional information to Danish ethics committee

7. Biological material

No biological material will be collected

8. Information from patient charts

We will ask patients permission to look up weight, height, medicine and prior illnesses from their chart. We will also ask permission to look up admission 12 months following last treatment. This is required to monitor adverse events.

9. Handling of patient information

All patient data will be safely stored in accordance with Danish legislation. Approval from the data protection agency will be obtained.

14. Research ethics

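### A single disclosed block size of 6, with unblinded treating doctors in the same department as the recruiters, lets a recruiter who learns earlier arms predict some allocations

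*Protocol*

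**What the plan says.** The Protocol, under Sequence generation, states: "A computer will generate the numbers using blocks of 6". It does not vary the size or keep it from recruiters. Allocation concealment mechanism says that the allocation is kept inside software.

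Under Implementation, the data manager generates the sequence, and "Doctors at the urogynecological clinical will enroll patients and assignment will occur when patient data is submitted in the electronical case report form". Interventions puts eligibility and consent before assignment: "Patients, who meet inclusion criteria and consent to study participation, will be randomized by computer service". Consent or assent adds: "Written and oral consent will be obtained and documented recruiting gynaecologist or specialized nurse in the outpatient clinic". Under Recruitment, all urogynaecologists and specialised nurses of the department take part in including women.

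Treatment, active or sham, is given by colleagues in the same department: "treatments will be performed by specialist gynecologists employed in the department". Blinding (masking) says "The patient and the outcome assessor (nurse) will be blinded" but that "the doctor performing the laser treatment cannot be blinded". Auditing says: "No auditing is planned as the procedures and measurements will be carried out by very few health workers".

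No section says whether a doctor who treats may also recruit, or who may see the arms of women already randomized.

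**The concern.** Hiding the list protects the next entry from being read. It does not stop someone who knows the block size and the earlier arms in the block from working out what must, or is likely to, come next. A published fixed size supplies the first item. Unblinded doctors in a small department could supply the second.

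A recruiter who expects a given arm may, even without meaning to, hurry, delay or withhold the enrolment of a particular woman. Blinding the patient and the assessor cannot undo a selection made before assignment. Statistical methods describes the primary comparison as a t-test on post-treatment scores, so a baseline difference created in this way would pass into that comparison. With 20 women per arm, a few steered enrolments would count.

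**Working it through.** The plan gives no predictability figure, so there is none to reproduce.

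**Inputs.** Block size 6 (Sequence generation). 20 women per group, 40 in all, with 1:1 allocation taken as implied (Sample size). One department, May 2019 to May 2020 (Eligibility criteria). Randomization at visit 1, first treatment at visit 2, and the later visit intervals (Participant timeline).

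**1. One block.** There are C(6,3) = 20 equally likely orders. Suppose a recruiter knows the place in the block and m earlier arms in it:

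| m | next arm certain | best guess right |
|---|---|---|
| 0 | 0 | 0.5 |
| 1 | 0 | 3/5 = 0.6 |
| 2 | 0 | 0.4 × 3/4 + 0.6 × 1/2 = 0.6 |
| 3 | 2/20 = 0.1 | 0.1 + 0.9 × 2/3 = 0.7 |
| 4 | 8/20 = 0.4 | 0.4 + 0.6 × 1/2 = 0.7 |
| 5 | 1 | 1 |

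**2. All earlier arms known.** 40 women fill six blocks plus four slots of a seventh.
- Certain: 6 × (0.1 + 0.4 + 1) + 0.1 = 9.1, and 9.1/40 = 22.8%.
- Best guess right: 6 × 4.1 + (0.5 + 0.6 + 0.6 + 0.7) = 27.0, and 27.0/40 = 67.5%.

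**3. Latest k arms unknown.** Slot i of a block then has m = max(0, i − 1 − k).

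| k | certain | best guess right |
|---|---|---|
| 1 | 6 × 0.5 = 3.0 (7.5%) | 6 × 3.6 + 2.2 = 23.8 (59.5%) |
| 2 | 6 × 0.1 = 0.6 (1.5%) | 6 × 3.4 + 2.1 = 22.5 (56.3%) |
| 3 | 0 | 6 × 3.2 + 2.0 = 21.2 (53.0%) |
| 5 | 0 | 20.0 (50%) |

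**4. Only some arms known.** Assume each earlier arm is known independently with probability p, so that m is binomial. For p = 1/2, 1/3 and 1/4, certain slots are 2.8%, 0.8% and 0.4%, and best guesses are right 58.2%, 55.9% and 54.6% of the time.

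**5. Where the trial may lie.** The gap between visits 1 and 2 is not given. Assume even enrolment with all visits inside 365 days. From the Participant timeline, visits 2 to 5 take 20 + 20 + 30 = 70 to 40 + 40 + 60 = 140 days. That leaves 295 to 225 days for 40 women, or one every 7.4 to 5.6 days. Each week of gap then hides about one arm, and three weeks hide about three to four (21/7.4 = 2.8; 21/5.6 = 3.8).

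**6. Varying sizes.** Sizes 4, 6 and 8 were drawn with equal chance in 6,000 simulated trials, against a guesser who knows the set of sizes:

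| k | certain, fixed 6 | certain, 4/6/8 | right, fixed 6 | right, 4/6/8 |
|---|---|---|---|---|
| 0 | 22.8% | 2.4% | 67.5% | 67.6% |
| 1 | 7.5% | 1.5% | 59.5% | 59.4% |
| 2 | 1.5% | 0.7% | 56.3% | 56.3% |
| 3 | 0% | 0.15% | 53.0% | 53.1% |

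**7. Balance at 40.** Fixed blocks of 6 give 20:20 in 60% of trials and 21:19 in 40%. Sizes 4/6/8 give 20:20 in 72%, 21:19 in 27% and 22:18 in 0.3%. At 22:18 the information kept is 4 × 22 × 18 / 1600 = 0.99.

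**The case against.** The strongest reply is that the block size is not the main lever. Varying it leaves the best-guess rate where it was, and a recruiter can be swayed by a good guess as well as by a certainty. This stands, and it is why the fix cannot stop at the block size.

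Second, the 22.8% ceiling needs no delay and one recruiter who knows every arm. Recruitment is spread over many staff, and the text on consent describes women being scheduled for treatment, with time to confer meanwhile. This also stands. The ceiling is a bound and should not be read as an estimate.

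Third, safeguards exist. The data manager holds the sequence, assignment follows form submission, consent and eligibility come first, and several entry criteria are measured. The patient, who reports the primary outcome, is blinded. These reduce the room for steering but do not prevent prediction from known arms. User rights in REDCap are a set-up matter, and silence about them does not show that they are unset.

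Some stronger readings are tempting but not supported:
- A reader might infer that the same doctor enrols and treats. The protocol leaves this possible but does not state it.
- A reader might infer a group of recruiting nurses who know the arms. The assessing nurse is blinded, and recruiting nurses may be those same nurses.
- A reader might infer that the baseline stress test could follow assignment. Data collection methods lists it as baseline data, and baseline information is registered at visit 1. In any case it has no bearing on prediction.

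**Conclusion.** The point holds as a modest, inexpensive improvement to a stated design choice. A fixed, disclosed block size, unblinded treating doctors in the recruiters' own department, and no text on role separation or on who sees earlier arms together allow some allocations to be predicted.

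The bounds are 22.8% certain and 67.5% of guesses right with full, immediate knowledge, and 0% and 50% if recruiters learn no arms. Because arms surface to treating doctors at visit 2, the lower part of the range is more realistic. The exact place cannot be fixed without the visit 1 to 2 gap and the actual staffing.

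The figures assume 1:1 allocation, 40 women and a recruiter who knows the place in the block. They measure predictability only. They do not show that selection occurred or would occur, and the protocol gives no basis for a bias in ICIQ points. Nor do they show that concealment of the list fails.

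**What to change.** - Replace the fixed size under Sequence generation with randomly varying block sizes (for example 4, 6 and 8). The data manager alone should know the sizes and their order. At full knowledge this cuts certain slots from 22.8% to about 2%. It brings no gain once three or more arms are unknown.
- Because varying sizes do not lower best-guess accuracy, also state that REDCap rights show a woman's arm only to the doctor who treats her.
- Where the existing roster allows, state that treating doctors do not judge eligibility or take consent.

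The cost is a generator setting, a user-rights setting and some rostering. Rostering is the real burden, since all urogynaecologists are expected to recruit. If it cannot be staffed, the first two changes are still worth making. Loss of balance is negligible: at worst 22:18, which costs 1% of the information.

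### The primary analysis is fixed as an unadjusted t-test on post-treatment ICIQ-SF scores although baseline ICIQ-UI SF is recorded: valid, but it gives up precision that a 40-patient trial needs

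*Protocol*

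**What the plan says.** Under Outcomes the protocol defines the endpoint: "Primary outcome of the study is patient experienced improvement of SUI evaluated by standardized ICIQ-SF questionnaire". Under Statistical methods it fixes the test: "The post treatment scores will be compared using Students t-test for the primary outcome and chi square test for dichotomous outcomes". That section names no covariate, change score or other use of the starting value, and puts the clinically relevant difference at about 2 points.

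The starting value is nevertheless available. Under Data collection methods: "Baseline data will be recorded: age, BMI, parity, ICIQ-UI SF, standardized stress test, degree of pelvic prolapse". ICIQ-SF severity is also an entry criterion, so every randomised woman should have a baseline score. (The protocol uses the names ICIQ-SF and ICIQ-UI SF; I read them as the same instrument.)

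Three design features bear on the point:

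- **Entry range.** Eligibility criteria admit women with mild to severe incontinence. The bands listed start at 1–5 and run up to 19–21.
- **Size.** Section 4, Sample size, says "20 patients in each group would be sufficient even with 20% dropout to show a difference", at a 0.05 significance level and 80% power.
- **Randomisation.** "A computer will generate the numbers using blocks of 6"; no stratification by severity is mentioned.

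**The concern.** A woman's score after treatment usually depends in part on where she started. An unadjusted comparison of post-treatment scores treats that part as noise. Here neither the analysis nor the randomisation makes use of baseline severity, and the endpoint is worded as improvement, which refers to a starting point.

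With about 16 to 20 women per arm and a 2-point target, precision is scarce. The possible cost is a wider confidence interval and lower power than the same data could give. Bias and false-positive error are not at stake.

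This is not a detail left open for a statistical analysis plan. The protocol names the primary test and the quantity it is applied to.

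**Working it through.** **Inputs**

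- Difference: 2 points (Sample size; Statistical methods).
- Alpha: 0.05, taken as two-sided because the protocol does not say.
- Women per arm: 20 planned, 20 × 0.8 = 16 after dropout (Sample size).
- SD: none is stated for the sample size. The Introduction reports, for one uncontrolled YAG-laser cohort, a "decrease of ICIQ scores from 12.0+/- 1.8 to 5.6+/-2.6". Reading the ± figures as SDs gives 1.8 at baseline and 2.6 at follow-up.
- Baseline to follow-up correlation r: not in the protocol; assumed to be 0.3, 0.5 or 0.7, with r = 0 as the worst case.

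**1. The plan's own figure.** It cannot be reproduced from stated inputs because the SD is missing, but it can be back-solved. With SD = 2.0, n = 2(1.960 + 0.842)² × 2.0² / 2² = 15.7, rounded up to 16, and 16/0.8 = 20. By the normal approximation, 16 per arm gives 80% power at SD 2.02; by the t distribution it does so at SD 1.95. I therefore show SD 1.95 (the plan's implied value) beside 2.6 (the only follow-up value quoted).

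**2. Validity.** In simulated trials with no treatment effect, both the t-test and ANCOVA rejected in about 5% of trials at every r from 0 to 0.7. Both estimate the same treatment effect.

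**3. Power.** For the t-test, the noncentrality is 2/(SD·√(2/n)) with 2n − 2 degrees of freedom. At SD 2.6 and n = 16 it is 2/(2.6 × 0.3536) = 2.18, which gives 55.8%.

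For ANCOVA, the residual SD is SD·√(1 − r²) with 2n − 3 degrees of freedom. The variance of the difference is multiplied by 1 + F/(2n − 2), averaged over F(1, 2n − 2), to pay for estimating the slope. On average this factor is 1 + 1/(2n − 4), or 1.036 at n = 16. Example at r = 0.5: residual SD 2.6 × √0.75 = 2.25, standard error about 2.25 × 0.3536 × √1.036 = 0.81, noncentrality about 2.47, power 66.6%.

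| SD | n per arm | t-test | ANCOVA r = 0 | r = 0.3 | r = 0.5 | r = 0.7 |
|---|---|---|---|---|---|---|
| 2.6 | 16 | 55.8% | 54.3% | 58.3% | 66.6% | 82.5% |
| 2.6 | 20 | 65.9% | 64.7% | 68.8% | 77.0% | 90.5% |
| 1.95 | 16 | 80% | 79% | 82% | 89% | 97% |

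Simulation with the covariate fitted agrees (SD 2.6, n = 16: 58.4%, 66.6%, 82.5%). Break-even at n = 16 is where (1 − r²)(1 + 1/28) = 1, that is r = √(1/29) = 0.19.

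**4. Precision and sample size at SD 2.6.** The mean 95% CI half-width at 16 per arm is 1.86 points for the t-test, against 1.81, 1.64 and 1.35 for ANCOVA at r = 0.3, 0.5 and 0.7. Women with data needed per arm for 80% power: 28, against 26, 22 and 16.

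**5. Chance baseline imbalance.** With baseline SD 1.8, the probability of a gap of at least k points is 2[1 − Φ(k/(1.8√(2/n)))]. For k = 1 it is 12% at n = 16 and 8% at n = 20; for k = 2 it is 0.2% or less. A 1-point gap would shift the unadjusted difference by the slope r × 2.6/1.8, which is 0.43, 0.72 and 1.01 points at r = 0.3, 0.5 and 0.7.

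**6. Change score as an alternative.** Its SD is √(SD₀² + SD₁² − 2r·SD₀·SD₁), where SD₀ is the baseline SD and SD₁ the follow-up SD. Power at 16 per arm for r = 0.3, 0.5 and 0.7:

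- equal SDs of 2.6: 43%, 56%, 78%, beating the planned test only above r = 0.5;
- SDs of 1.8 and 2.6: SD = √(10 − 9.36r), giving 53%, 66%, 84%, beating it only above about r = 0.35.

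**The case against.** The strongest reply is that nothing here is an error. The t-test is valid, the protocol does not contradict itself, and covariates are often settled in an analysis plan, which is not at hand. The validity point is right and limits the finding to efficiency. The analysis-plan point carries less weight, because the protocol names the primary test outright.

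Second, the benefit depends on a correlation that the protocol does not give. This stands. At r = 0.3 the gain is 2.5 points of power and 0.05 points of half-width (1.86 to 1.81), and below about r = 0.2 ANCOVA loses slightly.

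Third, the 55.8% and the 28 per arm come mainly from taking an SD of 2.6 from an uncontrolled cohort in which 19 women had stress incontinence. They are not caused by the t-test. This is also correct: at the implied SD of 1.95 the planned test meets its 80% target. The finding is therefore the gap between the two methods, which appears at both SDs. Whether the sample size is adequate is a separate question.

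Fourth, chance imbalance is already reflected in the t-test's standard error, so it should not be counted as a second cost. I agree. Step 5 shows only how the lost precision would appear in a single trial.

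Finally, a change score would do about as well as ANCOVA at r = 0.5 or more if the two SDs really are 1.8 and 2.6. That is true, but it rests on that SD ratio. ANCOVA estimates the slope and does not need the assumption.

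**Conclusion.** The point holds as a shortfall in efficiency. The primary analysis is valid but ignores a baseline measurement that the trial already collects.

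At 16 per arm and 2 points, adjustment adds about 2 points of power at r = 0.3, 9 to 11 at r = 0.5 and 17 to 27 at r = 0.7, across SDs of 1.95 to 2.6. The worst case, a baseline that predicts nothing, costs about 1.5 points. The direction is secure for any r above about 0.2. The size is not known, because r and the planning SD are not in the protocol; the figures also assume a two-sided test and 20% dropout. The change should be made, but the trial's conclusions would not be invalid without it.

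**What to change.** Replace the primary-analysis sentence in Statistical methods with wording to this effect: the ICIQ-SF score at the fifth visit will be analysed by ANCOVA with treatment group as factor and baseline ICIQ-SF as a continuous covariate; the adjusted mean difference will be reported with its 95% confidence interval; an unadjusted t-test will be given as a supportive analysis.

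Do not substitute a plain change-score t-test, since whether it beats the planned test depends on r and on the ratio of the two SDs. If pad leakage in grams is analysed, baseline grams can serve as covariate in the same way.

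The cost is one sentence and one degree of freedom, with no new data. The change must be made before outcome data are seen, so that the result cannot influence the choice of adjustment.
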